3. STUDY SYNOPSIS

Full study title:	VIVO™ non-invasive Time Assessment Protocol
Short study title:	VIVO™ mapping Protocol
Study R&D number:	VIVO-RBH01
Chief Investigator:	[name]
Medical condition/disease under investigation:	Patients undergoing PVC/VT Ablation with structurally normal hearts
Study duration:	9 months
Primary Objective:	
Safety:
 
 • Absence of acute adverse events due to the use of VIVO system during PVC/VT ablation • Safety endpoint of the entire mapping and ablation strategy 
Efficacy:
 
 • To assess the efficacy of VIVO to decrease procedure time as compared to standard of care ablation procedures.
Secondary Objective:	
 • To assess clinical outcome (suppression of reduction of PVCs burden/VT at 3-month F/U) • To assess economical outcome (cost reduction per case)
Study population:	
VIVO Cohort – 15 patients presenting for PVC/VT ablation with structurally normal heart
 
Control Cohort – Retrospective review of historical matched patients within the physician's database that had PVC/VT ablations with structurally normal hearts

Recruitment Target	15 patients
Recruitment Window (Months)	6 months
Methodology:	The study is a non-randomized, single-centre, study designed to evaluate the procedural efficacy of VIVO as compared to standard of care ablation procedures. Up to 15 patients will be enrolled.
Eligibility criteria:	
Inclusion criteria:
 
 1. Subjects who are at least 18 years or older 2. Subjects who are scheduled for PVC/VT ablation procedure 3. Subjects who have signed an IRB/EC approved Informed Consent Form and applicable subject privacy protection authorization per local law 4. Subjects will be selected without regard to gender or age (unless precluded by local regulatory requirements) 5. Subjects with or without cardiac structural disease
	
Exclusion criteria:
 
 1. Reversible causes of PVC/VT 2. Subjects with recent (within 3 months) acute coronary syndrome 3. Subjects who are contraindicated for CT or MRI (must be able to get one)

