4.3.2 Procedure Requirements

4.3.2a Prior to EP Procedure

Prior to the procedure the subject will undergo cardiac and thoracic imaging. This can be in the form of a MRI or CT scan, based on physician preference. Specific MRI and CT scan protocols do not significantly differ from the protocols already in use at the Brompton for pre-procedure roadmap scan. The recorded DICOM images should be provided the physician to upload into VIVO for future segmentation. The Mortara 12-lead Holter will be used to record the patient’s PVCs templates (with their respective frequency of presentation). The recorded files will be then imported into Vivo analysis software for the analysis and localization on the pre-reconstructed model. Likewise, the analysis will be done with templates from the Sensis software in the catheter laboratory.

The 3 D Camera will be used to take a 3D image of the patient’s torso after ECG lead placement. This will be merged with the cardiac anatomy from the 3D scan.

4.3.2b During the EP procedure

The EP procedure will be completed per the Institution’s standard of care using a 3D electroanatomical mapping system (CARTO, Biosense Webster).

The information from VIVO analysis will be integrated in the 3D mapping process such that the ablation procedure will be provided with this information, or in post-processing to establish the accuracy of the localization.

Pacing locations can be selected at any time during the procedure based on the physician’s preference.

4.3.2c Registration of EAM to Imaging

Left sided ablations: A Carto mapping catheter will be used to generate a complete fast anatomic map (FAM) anatomic shell of the left ventricle for identification of cardiac structures related to imaging. Imaging should be acquired at End Diastole. Landmarks will include those that are required for the individual procedure, including the papillary muscles if pacing is planned on the papillary muscles.

Right sided ablations: A Carto mapping catheter will be used to generate a complete fast anatomic map of the entire right ventricle and right ventricular outflow tract. Landmarks will include those that are required for the individual procedure.

4.3.2d Identifying the location of PVC or VT Origin

Identification with VIVO: Identifying the location of the PVC or VT foci with VIVO will be done prior to the patient's procedure.

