6. STUDY DESIGN

6.1 OVERALL DESIGN

This is a prospective, single arm, observational and feasibility study, which will recruit 15 non-selected patients, with structurally normal heart, with a conventional indication for catheter ablation of PVCs/VT. The follow up will be of three months. The study will also include another retrospective cohort, including age & gender matched patients, without cardiac structural disease, with a conventional indication for catheter ablation of PVCs/VT from the last 5 years' database of the same operator. For this second retrospective cohort there will be no follow-up.

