8. SUBJECT/PATIENT RECRUITMENT PROCESS

Patient recruitment at a site will only commence once the *study* team has ensured that the following approval/essential documents are in place:

1. HRA approval,
2. Local Site Delegation of Duties and Signature Log is completed (if applicable).

The Royal Brompton Hospital is the single site participating in the trial and will be asked to provide a copy of the following:

1. Signed Clinical *study* Site Agreement (CSSA) (if applicable)
2. Confirmation of capacity and capability

All subjects who wish to enter the study will be fully screened and consented by the Chief Investigator (CI), Principal Investigator or Co-Investigator.

We will recruit patients from those with PVC/VT who have already an indication for catheter ablation according to the current guidelines or have recurrent PVC/VT after previous catheter ablation(s). Patients will be offered participation in the study during the visit in the outpatient clinic. Only one centre will be involved in recruitment of the patients. All electrophysiology consultants in each Trust will be familiar with the protocol and be involved in selection of the patients.

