11.2 Radiology or any other procedure(s)

All patients will undergo a cardiac CMR or CT exam to be used as a roadmap during the ablation procedure. The CT exam will comprise of a standard-of-care contrast-enhanced scan to visualise the cardiac chambers. This pre-procedure imaging is necessary in order to define the spatial anatomical relationship of the cardiac chambers. In the event that the ablation procedure needs to be repeated during follow-up, the roadmap scans can be re-used.

As part of a conventional PVC/VT ablation procedure, the patient is exposed typically to about 2 mSv of ionizing radiation, occasionally increasing to 10 mSv or more, per procedure. If radiation is necessary to be used during any of the study procedures than efforts will be made to lower the exposure to as low as reasonably achievable including the re-use of the CT or CMR scan for 3D image integration during the ablation procedure(s).

- ***Techniques and Interventions***

The technique of mapping the ventricular chambers/epicardial space in order to guide the PVC/VT ablation is a conventional procedure which is carried out routinely in the catheter labs using different mapping system according to operators' experience and confidence. The here proposed study will use the Vivo™ (Catheter Precision, Inc., USA) in the pre-invasive phase in order to guide ablation.

- ***Tools***

All tools used for the ablation procedure will include standard materials for ablation of PVC/VT. The Vivo™ Anatomy and Analysis software and the Kinect Camera are fully CE marked.

- ***Study Drugs***

This section does not apply.

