14. STATISTICAL DESIGN

This is a prospective, non-randomised, observational study which will recruit 15 non-selected patients with PVC/VT eligible for catheter ablation, without structural heart disease.

Procedural outcomes will be compared to age & gender matched procedures of the same operator from the last 5 years' database.

The statistical design was decided in collaboration with the study PIs and will be descriptive only.

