14.1 SAMPLE SIZE AND RECRUITMENT

This is a feasibility pilot study, which will test the feasibility of PVC/VT foci mapping with Vivo system and catheter ablation in unselected patients without structural heart disease, eligible for PVC/VT ablation. Therefore, no power calculation has been done and the number of patient recruited will be of 15 which are deemed sufficient by the CI and Co-PIs on a clinical basis.

The estimated recruitment period for the trial will be of 6 months. We estimate that this sample size is attainable in practice, as the number of PVC/VT ablation procedures per year performed within the Trust is around 100. We also included patients with previous PVC/VT ablation in order to maximise chances of recruitment. This pilot is performed with the intention to plan a prospective multi-operator/multicentre trial which is adequately powered. We will aim to compare the procedure parameters as well as the outcome of this trial to age & gender matched procedures of the same operators from the last 5 years' database.

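### The control rule counts procedures rather than patients and is looser than VIVO-arm entry, so the primary procedure-time comparison can be biased in either direction

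*Combined protocol and SAP*

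**What the plan says.** The control group is described in five places, which do not agree.

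- **Section 14:** "Procedural outcomes will be compared to age & gender matched procedures of the same operator", over the last five years. Sections 14.1 and 14.3 repeat this and also count procedures. Section 14.1 refers to operators in the plural; 14 and 14.3 refer to one.
- **Section 6.1** counts people: "The study will also include another retrospective cohort, including age & gender matched patients, without cardiac structural disease". It adds a conventional indication for ablation.
- **Section 3 (synopsis)** also counts people, as a "Retrospective review of historical matched patients within the" physician's database, with structurally normal hearts. It names no matching variables.

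For the VIVO arm, section 8 admits patients whose arrhythmia has come back after an earlier ablation, and section 14.1 gives the reason: "We also included patients with previous PVC/VT ablation in order to maximise chances of recruitment". Section 4.3.2 has every VIVO case mapped with CARTO, including a fast anatomic map. Section 11.2 has every patient scanned by CMR or CT beforehand. On routine practice, section 11.2 says that mapping to guide ablation "is a conventional procedure which is carried out routinely in the catheter labs using different mapping system", and ties the choice to the operators' experience and confidence.

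Section 14.2.1 makes procedure time against usual ablation practice the primary efficacy endpoint. Section 5.2 uses the same historic controls for cost per case. Section 14 calls the design descriptive only, and section 14.6 adds no further considerations.

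**The concern.** The two cohorts enter by different rules, and the difference falls on features that could plausibly affect how long a procedure takes. If controls are procedures, one person can contribute more than once. A VIVO participant ablated by the same operator within five years can also be matched to themselves: gender agrees, age differs by at most about five years, and no age tolerance is stated. The cohorts would then be neither separate nor independent. Such a procedure would also be one after which the arrhythmia returned, which matters for the outcome comparison planned in section 14.3.

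Separately, a comparison of VIVO plus CARTO plus a scan with a group of unknown mapping and imaging does not isolate VIVO. The result would feed into the cost comparison and into the larger powered trial that section 14.1 has in view.

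**Working it through.** **1. The rules side by side**

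| Feature | VIVO arm | Controls as written |
|---|---|---|
| Unit | Patient | Patient (3, 6.1); procedure (14, 14.1, 14.3) |
| Procedures per person | One index procedure | No limit stated |
| Overlap with VIVO participants | – | Not excluded |
| First or repeat ablation | Both allowed (8, 14.1) | Not mentioned |
| Mapping system | CARTO (4.3.2b) | Not mentioned |
| Pre-procedure CT/CMR | All (11.2) | Not mentioned |
| Section 7.2 exclusions | All | Structural disease only (3, 6.1) |

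**2. How common could self-matching be?** Section 14.1 gives about 100 procedures a year for the whole Trust, so five years hold about 100 × 5 = 500. If all 15 participants had one earlier procedure there, that is 15/500 = 3% of the pool. Under random selection of 15 controls it is 15 × 0.03 = 0.45 of a control. One operator's pool is smaller than 500 by an amount not given, so the share could be higher there or after matching.

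**3. Direction and scale of bias.** The plan has no procedure time, standard deviation (SD), repeat share, mapping-system share or scan share, and no figure of its own to reproduce. The following is illustration only. Let f_c and f_v be the shares of affected procedures among controls and VIVO cases, and D their excess time in SD units. Then

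bias = f_c × D − f_v × D (positive favours VIVO).

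Assuming 15 v 15, no true effect and a two-sided 5% test (the plan names no test for procedure time), the chance of a significant result in VIVO's favour is Φ(bias/√(2/15) − 1.96), where √(2/15) = 0.365. With no bias it is 2.5%.

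| f_c | f_v | D | Bias (SD) | Chance in VIVO's favour |
|---|---|---|---|---|
| 0.10 | 0 | 0.5 | 0.05 | 3.4% |
| 0.20 | 0 | 1 | 0.20 | 7.9% |
| 0.33 | 0 | 1 | 0.33 | 14.5% |
| 0.20 | 0.20 | 0.5 | 0 | 2.5% |
| 0.33 | 0 | −0.5 | −0.17 | 0.8% |
| 0 | 0.33 | 0.5 | −0.17 | 0.8% |

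The last three rows matter as much as the first three. Equal shares of repeat cases cancel. If affected control procedures were shorter, or if repeats are longer and sit mainly in the VIVO arm, the comparison turns against VIVO. All f, D and the 1:1 ratio are assumptions.

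**The case against.** The strongest reply is that the gap exists only by silence. Section 6.1 speaks of another cohort of patients and the synopsis lists a separate control cohort, so different people were probably meant. Self-matching also needs the same operator, the five-year window and selection as a match, and no text says that any participant meets all three. This makes overlap less likely, but the three statistical sections that would be applied do not rule it out.

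On mapping and imaging, section 4.3.2 presents CARTO as the site's usual practice and the scan protocols as already in use, and the schedules in 6.3 and 10.5 mark the scan as routine. The variation described in 11.2 is linked to operators, and controls come from the same operator. This weakens the point on mapping system and scan. It does not remove it, because use over five years is not documented and 14.1 allows more than one operator.

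Some 7.2 exclusions, such as willingness to attend follow-up, mean nothing for a cohort that section 6.1 does not follow up. That is right, and only exclusions that can be checked from records are at issue.

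Finally, this is a 15-patient feasibility pilot with no power calculation. That limits the consequences, but selection shifts a descriptive mean as much as a tested one.

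A reader might go further and infer that earlier failed procedures, or cases without CARTO or a scan, ran longer and so lengthen control times in VIVO's favour by some number of minutes. The documents do not support this. They report no procedure time for any kind of case, and repeat ablations are expressly allowed in the VIVO arm, where they could push the difference the other way.

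**Conclusion.** The concern holds as a defect in the control-eligibility rule, without a stated direction. Sections 14, 14.1 and 14.3 conflict with 3 and 6.1 on the unit. The rule as written permits repeated use of one person, including a VIVO participant. It leaves first or repeat status, mapping system, scan and most of the 7.2 exclusions uncontrolled. The primary procedure-time comparison can therefore be biased either way. The size is unknown, and the SD-unit figures above show only how it would behave under assumed inputs. The unit, the overlap and first versus repeat status are the firmer parts. Mapping system and scan are weaker, because both are described as existing practice. The rule should be corrected before controls are drawn.

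**What to change.** Amend sections 6.1, 14, 14.1 and 14.3 so that they give one control rule:

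- The unit is the patient, with one procedure per control patient, selected by a rule fixed before any procedure times are seen.
- Nobody enrolled in the VIVO cohort can be a control.
- The section 7.2 exclusions that can be checked from records apply to controls.
- Controls are CARTO-mapped with a pre-procedure CT or CMR where available. Otherwise mapping system and scan are reported by cohort.
- First versus repeat ablation is either a matching variable or a split by which the time comparison is reported. Without this, the imbalance that could run in either direction would remain even after overlap is barred.

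The cost is rewording and a somewhat smaller control pool. The VIVO sample of 15 does not change. The documents do not describe what the database holds, so whether each item is recorded should be confirmed before the rule is fixed.

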5.2 SECONDARY OBJECTIVES

We will assess the efficacy of Vivo non-invasive mapping system guided ablation with regards to safety and clinical outcome. Furthermore, we will assess if the precise 3D a priori knowledge of the arrhythmia exit site shortens the procedure and how large thereby the reduction of costs per single case is, as compared to historic controls.

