14.2 ENDPOINTS

14.2.1 Primary endpoints

Safety:

- Absence of acute adverse events due to the use of VIVO system during PVC/VT ablation
- Safety endpoint of the entire mapping and ablation strategy

Efficacy:

- To assess the efficacy of VIVO to decrease procedure time as compared to standard of care ablation procedures.

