14.3 STATISTICAL ANALYSIS PLAN

Descriptive statistic data with regard to baseline and procedural variables will be reported; continuous variables will be expressed by mean \pm standard deviation or median and interquartile range (25th, 75th percentile), depending on the normality of distribution; categorical variables will be summarized by frequencies and percentages. The outcome of radiofrequency ablation on the entire cohort of patients will be presented in the form of percentage of patients free from symptomatic or documented arrhythmia or with only mild symptoms related to arrhythmia recurrence.

Depending on the severity of symptoms and documentation of tachycardia during follow-up, patients will be divided into two groups (success/recurrence). Baseline characteristics and procedural variables will be compared between these two groups by student t-tests, Mann Whitney U tests, or Fisher's exact test where appropriate in order to identify those variables associated with better mid/long term outcomes. A two-tailed p value <0.05 will be considered statistically significant. Intra-patient improvement from baseline to 6 months follow-up visit will be assessed by McNemar's test. Freedom from PVC/VT will be assessed as a time-dependent variable using Cox proportional hazard models.

To judge if ablation strategy using Vivo mapping system is as successful in achieving the clinical endpoint, we will compare the procedure parameters as well as the outcome of this trial to age & gender matched procedures of the same operator from the last 5 years' database.

To measure the strength of association between the acute successes (PVC/VT suppression at the end of the ablation) and outcome, a McNemar test will be performed. Data will be analyzed using SPSS version 18 (IBM Corporation).

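### Controls come from the same operator's last five years, and procedure date is neither matched nor analysed, so any calendar trend in procedure time, in either direction, is attributed to VIVO

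*Combined protocol and SAP*

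**What the plan says.** The primary efficacy endpoint in section 14.2.1 is "To assess the efficacy of VIVO to decrease procedure time as compared to standard of care ablation procedures".

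The comparator is described in several places:
- Section 14: "Procedural outcomes will be compared to age & gender matched procedures of the same operator from the last 5 years".
- Section 6.1: "another retrospective cohort, including age & gender matched patients, without cardiac structural disease, with a conventional indication for catheter ablation of PVCs/VT", from the same operator's last five years.
- Synopsis: "Retrospective review of historical matched patients within the" physician's database.
- Section 5.2, on procedure length and cost per case: "as compared to historic controls".

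The matching factors named are age and gender. Controls must also share the operator and have no structural heart disease. Section 14.1 refers to operators in the plural where the other sections have one operator; these should be reconciled.

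On analysis, section 14.3 says "we will compare the procedure parameters as well as the outcome of this trial to age & gender matched procedures" but names no test, model or covariate for that comparison. Its t, Mann-Whitney and Fisher tests compare patients with success and patients with recurrence, and its Cox model concerns freedom from arrhythmia. Section 14.6 adds nothing. Section 14 calls the design descriptive.

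On size and timing, section 14.1 says "no power calculation has been done and the number of patient recruited will be of 15" and "The estimated recruitment period for the trial will be of 6 months".

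**The concern.** The VIVO cases fall in one recruitment period, and the controls are described throughout as retrospective or historical. Group and calendar period are therefore nearly the same variable. Restricting to one operator removes differences between operators. It leaves that operator's own change over time, and any change in the laboratory, inside the VIVO contrast.

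At stake is the reading of the primary efficacy endpoint and of the cost reduction per case, which section 5.2 ties to the same controls. Section 14.1 also says the pilot is meant to lead to an adequately powered multicentre trial. As an illustration, if a true saving of 20 min appeared as 30 min and that trial were sized on 30, it would have (20/30)² = 0.44 of the patients it needs.

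**Working it through.** The plan contains no calculation to reproduce. The first check is whether procedure date enters the design or analysis anywhere. The sections listed above, read together, give age, gender, operator and absence of structural disease as the only selection factors, and no analysis term for date.

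The second check is how large the effect could be.

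**Inputs from the documents:** a five-year control window (sections 6.1, 14, 14.1, 14.3), a 6-month recruitment period and 15 VIVO patients (section 14.1).

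**Assumptions:** the control window ends when VIVO recruitment starts (the plan gives no start or end date); controls and VIVO cases are each spread evenly over their periods; VIVO has no true effect; mean procedure time in the VIVO period is 180 min.

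**Mean lag.** 5/2 + 0.5/2 = 2.5 + 0.25 = 2.75 years. It would be shorter if the matches cluster in recent years and longer if they cluster early.

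**Spurious saving** for a fall of a fraction r per year: 180 × [(1 − r)^(−2.75) − 1].
- r = 0: 0 min
- r = 0.02: 10.3 min
- r = 0.05: 27.3 min

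Averaging over the whole window instead of using the mean lag gives 10.4 and 27.8 min, so the shortcut is adequate. With 150 min and r = 0.02 the figure is 8.6 min.

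**Opposite trend**, times rising by r per year: 180 × [(1 + r)^(−2.75) − 1].
- r = 0.02: −9.5 min
- r = 0.05: −22.6 min

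Here VIVO would look slower than it is. None of these biases shrinks as controls are added; more controls only make the biased difference look more precise.

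**Limiting controls to the last 24 months.** Mean lag = 2/2 + 0.25 = 1.25 years. The remaining bias is 180 × [(1 − r)^(−1.25) − 1] = 4.6 min at 2% and 11.9 min at 5%. With an even spread, 24/60 = 40% of controls are kept, which is 6 out of 15.

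**Precision cost of a linear date term.** Assume equal SDs and a slope estimated from n controls whose dates have variance 5²/12 = 2.083. Since 2.75²/2.083 = 3.63, the ratio of standard errors is √{[1/15 + 1/n + 3.63/n] / [1/15 + 1/n]}.

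| Controls (n) | Ratio | Wider by |
|---|---|---|
| 15 | 1.68 | 68% |
| 30 | 1.49 | 49% |
| 60 | 1.31 | 31% |
| 150 | 1.15 | 15% |

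The plan states neither the number of controls nor a matching ratio, so all four rows are shown.

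**The case against.** The strongest defence is that this is a descriptive pilot of 15 patients with no power calculation, that the same operator is used on purpose, and that no section reports any trend in procedure time. A strict rule for claiming a saving would not suit such a study.

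Part of this stands. A reader might infer that the operator became faster, or that equipment and workflow changed, and hence that the plan will show a saving where none exists. The documents do not support that: they report no such change, and the trend could be nil or the reverse. A reader might also infer that a linear date term would settle the matter. It would not, because no control is concurrent: the adjusted estimate extrapolates the control trend beyond its range and would miss an abrupt or curved change. It is also expensive with few controls. Nor do the documents list the database's fields. That dates can be retrieved is an inference, though selecting a five-year window requires them.

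What does not stand is the idea that descriptive or pilot status removes the problem. A descriptive difference in means carries the same bias as a tested one, and this difference addresses the primary efficacy endpoint.

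**Conclusion.** The concern holds as a gap in design and analysis: VIVO use is almost fully confounded with calendar time, and the plan neither limits nor displays this. That rests on the text alone. The size and direction cannot be determined from the documents. The range of 0 to about 27 min of spurious saving, and the reversed sign under a slowing trend, depend on the assumed 180 min, the assumed 0% to 5% per year and the even spread of controls. The conclusion is that a saving found under this plan could not be told apart from a calendar trend. It is not that such a saving would be false.

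**What to change.** Amend sections 14 and 14.3 before the controls are extracted:

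1. Record the procedure date of every control, and state the start and end of the five-year window.
2. Among eligible age and gender matches, choose the procedures closest in date to the VIVO cases.
3. Plot procedure time against date in the controls, and list the 15 VIVO cases in date order.
4. Report the VIVO-control difference with a pre-specified sensitivity analysis limited to controls from the most recent 24 months. If step 2 already yields only such controls, the two analyses coincide, and the report should say so.
5. A date-adjusted estimate may be shown as supporting analysis, with a statement that it extrapolates the control trend.
6. If these estimates differ materially, report that the saving cannot be separated from a calendar trend.

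The cost is plan wording, one extra data column, fewer usable controls and less precision. The 24-month window shortens the lag but leaves some bias, as shown above, and should be reported with that limitation. Section 14.1 puts Trust volume at about 100 procedures a year, so a recent window may be workable, but the study operator's share is not stated and should be checked first. Patients and recruitment are unaffected.
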